## STUDY MANAGEMENT

Before the recruitment and enrollment of participants, the participating study site must have the protocol and consent form approved by their local Institutional Review Boards (IRBs). In addition, study site must receive protocol registration approval from the ATN Coordinating Center (CC) by submitting a complete registration packet with the site's IRB approved documents and a site registration form. All original approved documents must be maintained at the clinical site.

All queries for this protocol should be sent to the ATN (151) project team using the ATN Protocol Query and Notification System (QNS) accessible via the ATN website (<https://sites.cscce.unc.edu/atn/>). The appropriate team member will respond to queries generally within 48 business hours via the ATN QNS. The Protocol Manager, with the help of other ATN CC personnel, Protocol Chair and/or NICHD, if necessary, will answer queries related to general protocol implementation, eligibility and CRF completion. The Protocol Chair or his/her designee will respond to study and participant management, exemptions and/or untoward event queries. This study follows the ATN Policy for Guidance for Safety and Impact Reporting. Queries and replies will automatically be archived at the ATN CC. The CC will post those queries deemed relevant to all sites on the ATN 151 FAQ page, where they will be available for future reference.

This study will use the Audio Computer-Assisted Self-Interview (ACASI) to collect study data. All questions related to the ACASI should be directed to the ATN Help Desk at the ATN CC by calling the toll-free ATN ACASI helpline at 1 [contact] or by email ([[contact]](mailto:[contact])).

For protocol registration issues, contact the ATN Coordinating Center [[contact]](mailto:[contact]).

## LIST OF ABBREVIATIONS AND DEFINITION OF TERMS

ACASI	Audio Computer Assisted Self Interview
AEs	Adverse Events
AFC	AIDS Foundation Chicago
AIDS	Acquired Immunodeficiency Syndrome
ATN	Adolescent Medicine Trials Network for HIV/AIDS Interventions
CAB	Community Advisory Board
CDART	Carolina Data Acquisition and Reporting Tool
CDC	Centers for Disease Control and Prevention
CFR	Code of Federal Regulations
CGSHP	Lurie Children's Hospital Center for Gender, Sexuality and HIV Prevention
Ci3	Center for Interdisciplinary Inquiry & Innovation in Sexual and Reproductive Health
CRF	Case Report Form
CT	Chlamydia
DHHS	U.S. Department of Health and Human Services
CC	ATN Coordinating Center
eCRF	Electronic Case Report Form
GC	Gonorrhea
GEE	Generalized Estimating Equations
HBM	Health Belief Model
HIPAA	Health Insurance Portability and Accountability Act
HIV	Human Immunodeficiency Virus
HRSA	Health Resources and Services Administration
IATA	International Air Transport Association
ICH	International Conference on Harmonization
iFOUR	Increase Individual Income and Independence Program
IRB	Institutional Review Board
LGBT	Lesbian Gay Bisexual Transgender
MATEC	Midwest AIDS Training and Education
MSM	Man who has sex with men
NICHD	National Institute of Child Health and Development
NIDA	National Institute on Drug Abuse
NIH	National Institutes of Health

[figure not shown]
OHRP	Office of Human Research Protection
OSHA	Occupational Safety and Health Administration
PI	Principal Investigator
PrEP	Pre-Exposure Prophylaxis
QA	Quality Assurance
QNS	Query and Notification System
RA	Research Assistant
SE Model	Supported Employment Model
SAEs	Serious Adverse Events
SID	Study Identification Number
SMC	Study Monitoring Committee
SPSS	Statistical Package for the Social Sciences
STI	Sexually Transmitted Infections
T1	Baseline study visit
T2	Post-Intervention study visit
T3	Month 8 follow-up visit
UC	University of Chicago
UEs	Untoward Events
UNC	University of North Carolina
YMSM	Young Men Who Have Sex with Men
YTW	Young Transgender Women

## STUDY ABSTRACT

[figure not shown]
DESIGN:	Work2Prevent will advance the science by adapting, tailoring, and pilot-testing a novel social and structural-level HIV intervention for YMSM and YTW of color ages 16-24 aimed at increasing economic stability (i.e., employment) through youth empowerment and asset development, and decreasing HIV risk behaviors (i.e., sex work) associated with social and economic marginalization.
DURATION:	Pilot-testing will last approximately 22 months
POPULATION:	All focus group, pilot-test, and the majority of key informant interview study participants will be Black/African American and/or Hispanic/Latinos males and transgender women (those assigned male at birth), ages 16-24 who identify as either: (1) a man who has sex with men (MSM) and/or gay or bisexual man; or (2) a transgender woman and/or transsexual male-to-female/transwoman. Additionally, key informant interview study participants will be any race/ethnicity and sex/gender, but will be identified as an employer and/or hiring manager of an LGBT-inclusive company.
STUDY INTERVENTION:	Intervention will consist of a series of 4 workshops that promote job seeking self-efficacy and job readiness. These workshops will be adapted from the existing iFOUR curriculum, a job readiness program for transwomen developed by the Chicago House. The iFOUR curriculum will be adapted based on feedback from the CAB, focus groups, and key informant interviews.
DATA COLLECTION:	Data will be collected through transcribed, digital audio-recorded interviews, ACASI, and eCRFs.
PRIMARY OBJECTIVES:	Determine the essential components of a theoretically-driven and developmentally-appropriate employment intervention aimed at increasing job seeking self-efficacy and readiness among YMSM and YTW of color ages 16-24.
SECONDARY OBJECTIVES:	Review and adapt relevant intervention components from the existing evidence-based employment program for HIV-positive adults (iFOUR) to YMSM and YTW of color.
TERTIARY OBJECTIVES:	Refine and pilot-test the employment intervention. Refine and Pilot-test the intervention in community-based settings.
RISK/BENEFIT CATEGORY:	Minimal
MONITORING:	Routine team monitoring of any adverse impact of the study will rely on the ATN Protocol Query & Notification System, a real-time, web-based interactive reporting system. Sites will also record and enter in the study database, all untoward events associated with

study participation, which will be reviewed on the protocol team's implementation monitoring calls.

## STUDY SCHEMA

## STUDY VISITS

## 1.0 INTRODUCTION

### 1.1 Background

Young men who have sex with men (YMSM) and young transgender women (YTW) face enormous disparities. In particular, HIV risk and infection among YMSM and YTW remains a significant public health problem. Furthermore, YMSM and YTW experience social and economic marginalization, which leads to high rates of unemployment, sex work, drug use, homelessness, and HIV risk. Sex in exchange for money, drugs, and/or food among YMSM and YTW of color is a significant public health problem.

Adolescent sex work places YMSM and YTW at increased risk for STIs, HIV, poor mental health outcomes, and substance abuse. Interventions that trace and disrupt the pathways between social and structural determinants of HIV infection are needed. Structural-level interventions foster agency to allow individuals to act in their own and their communities' best interests, and have been positively associated with the uptake of behavioral and biomedical technologies, as well as the promotion of health-enabling environments. To date, few structural interventions targeting adolescent sexual and gender minorities exist, and we know of no studies that have explicitly examined the role of employment on HIV risk and prevention for YMSM and YTW. Employment as prevention has the potential to be a scalable intervention that can be deployed among at-risk YMSM and YTW.


Faced with few economic options and protections, YMSM and YTW may migrate to non-traditional economies or “street careers” as a means of survival. In a study conducted by Adolescent Medicine Trials Network for HIV/AIDS Interventions (ATN) members in Los Angeles ([name]) and Chicago ([name]) [Co-I for this proposal], 76% of 151 YTW ages 15-24 reported engaging in sex work, with 35% in the past 3-months(Auerbach, Parkhurst, & Caceres, 2011; Xavier, Bobbin, Singer, & Budd, 2005). Among HIV-positive YTW, 23% were involved in sex work—underscoring the link between adolescent sex work and HIV (Xavier et al., 2005). In a large study of YMSM of color (n=3,316, median age 19), roughly 12% reported engaging in sex work (past 6-months) (Melendez & Pinto, 2007). Sex work and HIV risk are further complicated by drug and alcohol abuse (Gayles et al., 2016). Scalable, low-cost, but potentially high impact, **structural-level interventions** that trace and disrupt the pathways between social and economic marginalization and adolescent HIV infection are sorely needed (Clements-Nolle, Marx, & Katz, 2006; Kammerer, Mason, Connors, & Durkee, 2001; Lomabrdi, Wilchins, Priesing, & Malouf, 2002). Structural interventions, such as comprehensive sex education, universal condom access, clean syringe exchange, and increased healthcare coverage have significantly reduced the incidence of HIV (Bockting, Miner, Swinburne Romine, Hamilton, & Coleman, 2013; Bradford et al., 2013; Clements-Nolle et al., 2006; Durso, Kastanis, Wilson, & Meyer, 2013; Grant et al., 2011; Kammerer et al., 2001; Lomabrdi et al., 2002; Reisner, Bailey, & Sevelius, 2014). The objective of the proposed study is to

target economic stability (i.e., employment) as a structural-level intervention for preventing adolescent HIV. The proposed study will adapt and pilot-test an effective theoretically-driven, employment program for HIV-positive adults (iFOUR) (*A Broken Bargain for LGBT Workers of Color*, 2013; Dyer et al., 2013; Fletcher, Kisler, & Reback, 2014; Kipke, Weiss, & Wong, 2007; Sifra Quintana, Roshenthal, & Krehely, 2010; Wilson et al., 2009) to the needs of at-risk YMSM and YTW of color, ages 16-24. This proposal is responsive to the NIH HIV/AIDS high priority topic by developing, testing, and implementing a new strategy to improve HIV prevention.

## **1.2 Rationale**

The goal of this project is to adapt, tailor, and pilot-test a novel social and structural-level HIV intervention for YMSM and YTW of color aimed at increasing economic stability (i.e., employment) through youth empowerment and asset development, and decreasing HIV risk behaviors (i.e., sex work) associated with social and economic marginalization.

The specific aims of this project are to:

1. Determine the essential components of a theoretically-driven and developmentally-appropriate employment intervention aimed at increasing job self-efficacy and readiness among YMSM and YTW of color ages 16-24.
2. Review and adapt relevant intervention components from the existing evidence-based employment program for HIV-positive adults (iFOUR) to YMSM and YTW of color.
3. Refine and pilot-test the employment intervention.
4. Refine and pilot-test the employment intervention in community-based settings

## **2.0 STUDY OBJECTIVES**

### **2.1 Primary Objective**

The primary objective is to determine the essential components of a theoretically-driven and developmentally-appropriate employment intervention aimed at increasing job seeking self-efficacy and readiness among YMSM and YTW of color ages 16-24. Up to 10 focus groups with YMSM and YTW of color who are currently employed or unemployed but seeking employment will inform the adaptation of the intervention. Key informant interviews with YMSM of color, YTW of color, and LGBT-inclusive employers will address intervention content.

### **2.2 Secondary Objective**

The secondary objective is to review and adapt relevant intervention components from the existing evidence-based employment program for HIV-positive adults (iFOUR) to YMSM and YTW of color. The study will assemble a community advisory board (CAB) of YMSM and YTW of color, youth-serving vocational specialists, employment training and placement experts, and sexual health educators to advise the investigative team on the translation of qualitative findings into curriculum adaptations.

### **2.3 Tertiary Objective**

The tertiary objective is to refine and pilot-test the employment intervention. All qualitative findings will be incorporated into a protocol with the iterative feedback of the CAB. Next, we will pre-test the Baseline visit, workshop sessions, and Post-Intervention visit with a sample of up to 5 participants. We will pilot-test the entire intervention among up to 70 at-risk YMSM of color and YTW of color and then in community-based settings with up to 40 at-risk YMSM of color and YTW of color in a single-arm pre/post trial,

assessing feasibility and acceptability. Study outcomes include: (1) job seeking self-efficacy and readiness; (2) employment; (3) HIV risk behaviors; and (4) STI and HIV infections.

## 2.4 Study Hypotheses/Research Questions

We hypothesize that this intervention will be both feasible and acceptable to the target populations and that the intervention will increase job self-efficacy and readiness, as well as decrease HIV risk behavior. This study will lead to a final intervention manual to be tested in an R01-type, large multi-site trial across the ATN study sites.

## 3.0 STUDY DESIGN

[figure not shown]
All research activities except for the community-based pilot will occur at the University of Chicago (UC), Center for Interdisciplinary Inquiry and Innovation in Sexual and Reproductive Health (Ci3). Ci3 is a foundation and federally funded research center focused on advancing adolescent sexual and reproductive health and rights through innovative research methodologies, intervention strategies, and novel solutions to broad social problems. Ci3 has a dedicated research team skilled in cross-disciplinary collaboration focused on adolescent health along with a broad network of community partners working with LGBT adolescents, and environments that will support the successful development, implementation, and evaluation of the project.

Community-based pilot-testing will be conducted by study staff in the community at the following organizations:

- The Village (Chicago Center of HIV Elimination, University of Chicago)
- TaskForce Prevention and Community Services
- Ann & Robert H. Lurie Children's Hospital of Chicago

Each community setting has a private area for the confidential conduct of the study, including study visits and workshop sessions.

**Conceptual Model:** Our conceptual model (Figure 1) draws on the existing iFOUR theoretical framework that operationalizes the Health Belief Model (HBM) and the Supported Employment Model (SE) to hypothesize the potential relationship between adolescent employment and HIV risk. We propose that employment, and subsequent economic connection and stability, serves as a structural-level intervention for adolescent HIV. Based on prior research, we hypothesize that the adapted and tailored iFOUR intervention will facilitate increased job seeking self-efficacy and job readiness [Path A] and ultimately increase employment placement and maintenance [Path B]. Further, we hypothesize that establishing economic stability will decrease engagement in HIV risk behaviors and increase HIV prevention and care [Path C], and decrease involvement with known social determinants of HIV (e.g., sex work, drug abuse) [Path D], that are directly linked to HIV transmission and acquisition [Paths E & F] among YMSM and YTW of color.

**Figure 1.** Conceptual Model

### 3.1 Study Population

All focus group, pilot-test, and the majority of key informant interview study participants will be Black/African American and/or Hispanic/Latinos males and transgender women (those assigned male at birth), ages 16-24 who identify as either: (1) a man who has sex with men (MSM) and/or gay or bisexual man or (2) transgender woman and/or transsexual male-to-female/transwoman. Additionally, key informants and study participants will be any race/ethnicity and sex/gender, but will be identified as an employer and/or hiring manager of an LGBT-inclusive company. Targeted Planned Enrollment tables contain the detailed breakdown for each recruitment and enrollment activity (Appendix III).

### 3.2 Sample Size

**Focus Groups:** We will recruit up to 80 YMSM and YTW of color, ages 16-24, to participate in one of up to 10 focus groups.

**Key Informant Interviews:** We will recruit up to 64 key informant YMSM (n=up to 12), YTW (n=up to 12), and LGBT-inclusive employers (n=up to 40) to participate in key informant interviews.

**Community Advisory Board:** Up to 12-member CAB of YMSM, YTW, youth-serving employment and vocational specialist, LGBT employment training and placement experts, and sexual health educators.

**Intervention Pre-Test:** We will pre-test the adapted employment intervention with a small sample of up to 5 YMSM of color and YTW of color.

**Intervention Pilot-Test:** We will pilot-test the adapted employment intervention with a diverse sample of up to 70 YMSM of color and YTW of color.

**Community Pilot-Test:** We will test the intervention with a sample of up to 40 YMSM of color and YTW of color in community-based settings.

### 3.3 Outcome Measures

Study outcomes include: (1) job seeking self-efficacy and readiness; (2) employment; (3) HIV risk behaviors; and (4) STI and HIV infections.

### 3.4 Biological Specimens

Project staff members who have completed mandatory training will conduct HIV/STI testing. Study participants will be screened for drug use and STIs such as chlamydia, gonorrhea, syphilis, and HIV

infection at the baseline and follow-up visits. Clinical specimens may include 15-20 mL first-catch urine, anal swab (GC,CT), oral/laryngeal swab, and finger stick. Participants with reactive STI or HIV tests will be referred to affiliated clinics at each site for evaluation and treatment. All participant referral clinics will be comprehensive and follow the Ryan White HIV/AIDS Programming instruction as developed by the HRSA HIV/AIDS Bureau. Senior Investigators are practicing physicians at study referral sites with experience in YMSM and YTW health, and will provide any subsequent mental health, medical case management, and psychosocial support service referrals as needed for participants. Following the protocols of our previous studies involving HIV testing, HIV-positive participants at follow-up will not receive HIV testing if they produce documentation of a previous diagnosis (e.g., medications, lab report). In addition, phase 3 participants with a known HIV positive status at the time of consent will not receive HIV testing at baseline or follow-up.

## **4.0 SELECTION AND ENROLLMENT OF STUDY PARTICIPANTS**

### **4.1 Inclusion Criteria**

#### **4.1.1 Focus Group Inclusion Criteria**

Must meet the following six criteria:

1. Male or assigned male at birth (YTW)
2. Identify as a man who has sex with men (YMSM) and/or gay bisexual man or transgender woman/transwoman
3. Identify as African American/Black, Hispanic/Latino, and/or a racial/ethnic minority or person of color
4. 16-24 years old
5. English-speaking (primary)
6. One of the following:
  - a. Currently employed
  - b. Unemployed but seeking employment

#### **4.1.2 Key Informant Interviews Inclusion Criteria for YMSM and YTW**

Must meet the following six criteria:

1. Male or assigned male at birth (YTW) [YMSM/YTW only]
2. Identify as a man who has sex with men (YMSM) and/or gay bisexual man or transgender woman/transwoman
3. Identify as African American/Black, Hispanic/Latino, and/or as a racial/ethnic minority or person of color
4. 16-24 years old
5. English-speaking (primary)
6. One of the following:
  - a. Currently employed
  - b. Unemployed but seeking employment

#### **4.1.3 Key Informant Interviews Inclusion Criteria for LGBT-Inclusive Employers**

Must meet the following four criteria:

1. Employers and/or managers at LGBT-inclusive companies which:

- a. Scored 80% or higher on the Human Rights Campaign, Corporate Equality Index 2015-2016 or
- b. Is a company currently listed as an Out & Equal, LGBT CareerLink employer or
- c. Is a non-profit organization with an LGBT-focused mission or
- d. Is an LGBT-owned small business (<200 employees) or
- e. Is a company or organization participating in an LGBTQ job fair

2. Located in the Chicago area
3. English-speaking
4. 18 years or older

#### 4.1.4 Phase 2 Intervention Pre Test & Pilot-Test Inclusion Criteria

Must meet the following eight criteria:

1. Male or assigned male at birth (YTW)
2. Identifies as a man who has sex with men (YMSM) and/or gay bisexual man or transgender woman/transwoman
3. Identifies as African American/Black, Hispanic/Latino, and/or as a racial/ethnic minority or person of color
4. 16-24 years old
5. English-speaking (primary)
6. HIV negative or of unknown status
7. Currently unemployed but seeking employment or employed only part-time 35 hrs or less on avg/wk)
8. Able to attend a 4-session employment program

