4.2. Secondary Outcomes

4.2.1. Change in Self-Reported Hours Worked Per Week (T1 to T3)

Hours worked per week will be self-reported at baseline and at the 8-month follow-up visit as any value between 0 and 99. Change in hours worked per week will be calculated by subtracting the baseline (T1) value from the 8-month follow-up (T3) value. Negative change indicates fewer hours worked per week, while positive change indicates more hours work per week.

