5. STATISTICAL ANALYSIS

5.1. General Considerations

The analytic plan is designed to determine preliminary efficacy of the intervention by comparing pre/post assessments of employment and sexual risk behaviors. Descriptive statistics will be used to analyze the proportions and central tendencies for participant sociodemographic covariates collected in the surveys. We will first generate frequencies, means, and other measures of central tendency as appropriate to describe our sample and outcomes at each of the three time points (baseline, post-intervention, and 8-month follow-up).

Changes in primary and secondary outcomes between baseline and 8-month follow-up will be assessed using paired t-tests for continuous variables and McNemar's test for matched categorical variables. We will use standard diagnostic tools to assess the appropriateness of the normality assumption (e.g., QQ-plots) and, if approximate normality of the residuals is not tenable, a non-parametric test for continuous paired data, i.e. Wilcoxon sign rank test will be used. All hypothesis testing will be done at an alpha-level of 0.1, given the exploratory nature of the study.

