2. SECONDARY OUTCOMES

2.1. SELF-REPORTED EMPLOYMENT

The primary employment outcome is based on the change in the number of self-report hours worked per week from T1 to T3.

2.1.1. Change in Self-Reported Hours Worked Per Week from Baseline to Month 8 Follow-Up (T1T3)

Description: Change in hours worked per week from Baseline to Month 8 follow-up (T1 to T3)

Variable: EMPHOUR_T1T3_1

Label: Change in Hours Worked per Week from T1 to T3 (T3-T1)

Type: Numeric; Range = -99 to 99

Algorithm:
If BSL9 = 0 then BSL27 = 0
If EXQ9 = 0 then EXQ27 = 0
EMPHOUR_T1T3_1 = EXQ27 – BSL27

If hours work per week at either time point is missing, then EMPHOUR_T1T3_1=Missing.

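### Change in hours worked is tested against zero in people admitted because they work few or no hours, so a significant rise is not by itself evidence of a workshop effect.

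*Protocol*

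**What the plan says.** Entry. Protocol 4.1.4 (Phase 2) requires participants to be "Currently unemployed but seeking employment or employed only part-time 35 hrs or less on avg/wk". Protocol 4.1.5 repeats this for Phase 3, and section 2.2 of each SAP carries it over.

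Outcome. SAP Phase 2, 4.2.1: "Hours worked per week will be self-reported at baseline and at the 8-month follow-up visit as any value between 0 and 99". The outcome itself is the T3 figure minus the T1 figure. Appendix 2.1 sets hours to zero for those not working at baseline ("If BSL9 = 0 then BSL27 = 0") and does the same at T3. Phase 3 is identical except that follow-up is at 3 months.

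Test. SAP 5.1: "Changes in primary and secondary outcomes between baseline and 8-month follow-up will be assessed using paired t-tests for continuous variables". If normality fails, "Wilcoxon sign rank test will be used". The level is given as: "All hypothesis testing will be done at an alpha-level of 0.1, given the exploratory nature of the study".

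Use. SAP 5.1 says that the analysis is meant to "determine preliminary efficacy of the intervention by comparing pre/post assessments of employment and sexual risk behaviors". Phase 3 says the same in nearly the same words, and Protocol 10.3.1 sets the same aim.

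Caveats. Protocol 10.2 and SAP 2.3 say that a comparison group was given up, in an exploratory study, to reduce variability. SAP 2.3 adds practice and fatigue effects. Neither document mentions that entry selects on the outcome.

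**The concern.** Baseline hours are confined by the entry rule to 0-35, while T3 hours may be 0-99. A participant who is out of work and looking for it starts at zero, so the change cannot be negative. Some of these job seekers would be expected to find work over the follow-up without any workshop. The value to compare with is the change that would have occurred anyway, and nothing in the plan says that this is zero.

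The fallback test does not help, because Wilcoxon also tests against zero. Nor does the adjustment in SAP 5.5 for baseline employment and attendance, because it does not supply the change expected without workshops.

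At stake is the reading of the outcome that Appendix 2.1 calls the primary employment outcome, in a programme whose purpose is to raise employment. Followed as written, the plan could report ordinary job finding as preliminary efficacy.

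**Working it through.** **The plan's own figure.** SAP Phase 2, 2.3 expects at least 50 of 70 to complete, about 70%: 50/70 = 71.4%, and 0.70 × 70 = 49. This reproduces. No power, effect size or SD is given. Phase 3 enrols up to 40 with no completion target; applying 70% gives 0.70 × 40 = 28, which is an assumption.

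**Possible range of change.** Lowest: 0 − 35 = −35 h. Highest: 99 − 0 = +99 h. For the unemployed the lowest is 0.

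**How much drift matters.** Take n = 50, two-sided alpha 0.10 (sidedness is not stated; two-sided is assumed) and an assumed SD of change of 15 h. The smallest significant mean rise is 1.677 × 15/√50 = 3.56 h (2.85 h at SD 12, 4.27 h at SD 18). If background drift is δ, the chance of a significant rise is 1 − F(1.677), where F is the noncentral t distribution with 49 df and noncentrality δ√50/15:

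| Drift δ (h/week) | 0 | 1 | 2 | 3 | 4 | 5 | 6 |
|---|---|---|---|---|---|---|---|
| P(significant rise) | 5% | 12% | 24% | 40% | 59% | 75% | 87% |

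**Where drift could come from.** All rates here are assumptions. Use a two-state employment model with monthly job finding f, monthly job loss l, m months (8 or 3) and share unemployed u at T1. New-job hours are uniform 10-40 (mean 25), part-time baseline hours are uniform 5-35 (mean 20), and 40% of part-timers still working have changed job.

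- Unemployed at T1 and working at T3: a = f/(f+l) × [1 − (1−f−l)^m].
- Working at T1 and out of work at T3: b = l/(f+l) × [1 − (1−f−l)^m].
- Drift = u·a·25 − (1−u)·b·20 + (1−u)(1−b)·0.40·5.

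Three Phase 2 settings:

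- u = 0.6, f = 3%, l = 5%: a = 0.375 × (1 − 0.92^8) = 0.183 and b = 0.625 × 0.487 = 0.304. Drift = 2.74 − 2.43 + 0.56, about +0.9 h. Significant rise in about 12% of simulated trials.
- u = 0.8, f = 8%, l = 3%: a = 0.727 × (1 − 0.89^8) = 0.441 and b = 0.273 × 0.606 = 0.165. Drift = 8.82 − 0.66 + 0.33 = about +8.5 h. Significant rise in over 99%.
- u = 0.4, f = 3%, l = 5%: drift = 1.83 − 3.65 + 0.84, about −1.0 h. Significant rise in about 1.5%, significant fall in about 13%.

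Crossing the full ranges (u 60-80%, f 3-8%, l 3-5%) gives about 12% to over 99% in Phase 2, with about 50% or more in 14 of 18 settings. Phase 3 gives about 11-71%. With u = 40%, Phase 2 gives about 1-55%.

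**Two cross-checks at n = 50, no workshop effect.**

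- Selection only: a population with stable average hours, sampled at 35 h or less. Over 16 assumed scenarios drift was always upward, +0.3 to +8.4 h, and a significant rise occurred in 6-95% (at least 50% in 7 of 16).
- Direct turnover: 30-70% unemployed, 10-50% of them working by T3, 20% or 40% of part-timers out of work by T3, 10% of part-timers moving to full time. A significant rise occurred in 0-99%, above 5% in 21 of 30 scenarios and at least 50% in 9 of 30. A significant fall was likelier than a rise in 8 of 30. The middle case (50% unemployed, 30% gaining work, 20% losing it) drifted +3.2 h, with a significant rise in 47% by t-test and 38% by Wilcoxon, and in 30% by t-test at n = 28.

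**The case against.** The strongest reply is that this is the admitted limitation under another name. Background change is what a missing control leaves unmeasured, and the plan says openly that it gave up the comparison group. The study is exploratory, hours is a secondary outcome, and the SAP's primary objective is feasibility and acceptability. Much of this stands, and it limits the weight of the point. It does not dispose of it: the caveats concern variability, practice and fatigue. None says that the entry rule selects on this outcome, and SAP 5.1 still directs the result to efficacy.

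Two stronger readings are tempting. One is that a false significant rise is likely. The documents give no share unemployed, no job gain or loss rate and no SD, and plausible inputs run from almost never to almost always. The other is that the entry rule fixes the direction of change. It does so only for the unemployed; part-timers are eligible and can fall by up to 35 h.

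The model also adds some drift by assumption, because each job change among part-timers gains 25 − 20 = 5 h on average. Without those changes, the 12% setting falls to 7%, and the 40%-unemployed setting shown above gives 0.1% rises against 29% falls.

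Nor do the documents say that the hours result will be used to plan the larger trial. Protocol 2.4 says only that the study leads to a manual to be tested there.

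**Conclusion.** The point holds in a limited form. The entry rule, the zero coding, the test against zero and the efficacy reading are all in the documents. Together they make zero the wrong no-effect value for change in hours, in both phases and under either test. With no workshop effect, a significant rise can occur well above the nominal 5%.

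Its frequency is not known. The ranges above rest wholly on assumed employment rates and hours, and on n = 28 for Phase 3. They show that the p-value cannot be interpreted without the background drift; they do not predict what this trial will find. The consequence is confined to one secondary outcome in a pilot, but that outcome is central to the programme's aim and the correction is cheap, so it should be made.

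**What to change.** In SAP 4.2.1, 5.1 and 5.5 of both phases, treat change in hours as descriptive. Report T1 hours, T3 hours and mean change with a 90% CI, overall and by baseline employment status (item 9 of the baseline questionnaire, which the Appendix already uses to set hours to zero).

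State that, because of the entry criterion, zero is not the value expected without the workshops, and that neither a p-value nor a CI excluding zero is to be read as preliminary efficacy for hours. The sentence about the CI is needed because a 90% CI excludes zero exactly when the two-sided 0.10 paired t-test rejects; replacing the test by the interval alone would leave the same inference on the page.

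Amend Protocol 10.3.1 (efficacy from pre/post employment) and 10.3.1.1 (paired tests for secondary outcomes) to match, since an SAP change alone would depart from the protocol.

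Cost: wording in two SAPs and a small protocol change, with no new data or visits. The price is a weaker claim for one secondary outcome.
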